14.4 Monitoring

Monitoring and auditing procedures developed or approved by Vertex will be followed, in order to comply with ICH GCP guidelines. On-site checking of the eCRFs for completeness and clarity, cross-checking with source documents, and clarification of administrative matters will be performed.

The study will be monitored by Vertex or its designee. Monitoring will be done by personal visits from a representative of Vertex (site monitor) who will review the eCRFs and source documents. The site monitor will ensure that the investigation is conducted according to the protocol design and regulatory requirements.

14.5 Electronic Data Capture

Vertex will provide the study sites with secure access to and training on the EDC application sufficient to permit site personnel to enter or correct information in the eCRFs on the subjects for which they are responsible.

An eCRF will be completed for each enrolled study subject. It is the investigator's responsibility to ensure the accuracy, completeness, clarity, and timeliness of the data reported in the subject's eCRF. Source documentation supporting the eCRF data should indicate the subject's participation in the study and should document the dates and details of study procedures, adverse events, other observations, and subject status.

The investigator, or designated representative, should complete the eCRF as soon as possible after information is collected. An explanation should be provided for all missing data.

The audit trail entry will show the user's identification information, and the date and time of any correction. The investigator must provide formal approval of all the information in the

eCRFs, including any changes made to the eCRFs, in order to endorse the final submitted data for the subjects for whom the investigator is responsible. This formal approval must be made via the EDC application.

Vertex will retain the eCRF data and corresponding audit trails. A copy of the final archival eCRF in the form of a CD or other electronic media will be placed in the investigator's study file.

14.6 Publications and Clinical Study Report

14.6.1 Publication of Study Results

Any and all scientific, commercial, and technical information disclosed by Vertex in this protocol or elsewhere should be considered the confidential and proprietary property of Vertex. The investigator shall hold such information in confidence and shall not disclose the information to any third party except to such of the investigator's employees and staff as have been made aware that the information is confidential and who are bound to treat it as such and to whom disclosure is necessary in order to evaluate that information. The investigator shall not use such information for any purpose other than for determining mutual interest in performing the study and, if the parties decide to proceed with the study, for the purpose of conducting the study.

The investigator understands that the information developed from this clinical study will be used by Vertex in connection with the development of the study drug and therefore may be disclosed as required to other clinical investigators, the US FDA, and to other government agencies. The investigator also understands that, in order to allow for the use of the information derived from the clinical study, the investigator has the obligation to provide Vertex with complete test results and all data developed in the study.

No publication or disclosure of study results will be permitted except under the terms and conditions of a separate written agreement between Vertex and the investigator and/or the investigator's institution.

14.6.2 Clinical Study Report

A clinical study report, written in accordance with the ICH E3 Guidelines, will be submitted in accordance with local regulations.

16 APPENDICES

16.1 The American College of Rheumatology Revised Criteria for Rheumatoid Arthritis

Four or more criteria must have been present at the time of diagnosis of RA. Criteria 1 through 4 must have been present for at least 6 weeks. Subjects with 2 clinical diagnoses are not to be excluded.

CRITERION	DEFINITION
1. Morning stiffness	Morning stiffness in and around the joints, lasting at least 1 hour before maximal improvement
2. Arthritis of 3 or more joint areas	At least 3 joint areas simultaneously have had soft tissue swelling or fluid (not bony overgrowth alone) observed by a physician. The 14 possible areas are right or left proximal interphalangeal joint (PIP), metacarpophalangeal (MCP), wrist, elbow, knee, ankle, and metatarsophalangeal (MTP) joints
3. Arthritis of hand joints	At least one area swollen (as defined above) in a wrist, MCP, or PIP joint
4. Symmetric arthritis	Simultaneous involvement of the same joint areas (as defined in 2) on both sides of the body (bilateral involvement of PIPs, MCPs, or MTPs is acceptable without absolute symmetry)
5. Rheumatoid nodules	Subcutaneous nodules, over bony prominences, or extensor surfaces, or in juxta-articular regions, observed by a physician
6. Serum rheumatoid factor	Demonstration of abnormal amounts of serum rheumatoid factor by any method for which the result has been positive in ≤5% of normal control subjects
7. Radiographic changes	Radiographic changes typical of rheumatoid arthritis on posteroanterior hand and wrist radiographs, which must include erosions or unequivocal bony decalcification localized to or most marked adjacent to the involved joints (osteoarthritis changes alone do not qualify)

References:

- 2. Primer on the rheumatic diseases. 13th edition. Klippel JH, Stone JH, Crofford LJ, White PH, editors. Appendix I, pg 670. Springer, 2008.

16.2 Washout Periods for DMARDs

	Washout Periods Before Screening if DMARD Recently Discontinued
DMARD – 1 DMARD REQUIRED (Anti-mala	rial allowed alone or with 1 other DMARD)
Leflunomide	28 days ^a
Methotrexate	45 days
Penicillamine	60 days
Sulfasalazine	45 days
Anti-malarial: Hydroxychloroquine/Chloroquine	28 days
NON-BIOLOGIC DMARD – MUST WASH O	UT
Azathioprine/ 6-mercaptopurine	45 days
Cyclophosphamide	60 days
Cyclosporine	60 days
Oral or injectable gold	60 days
Mycophenolate	60 days
BIOLOGIC DMARD – MUST WASH OUT	
Abatacept	60 days
Adalimumab	45 days
Anakinra	45 days
Certolizumab pegol	60 days
Etanercept	45 days
Golimumab	60 days
Infliximab	60 days
Rituximab/Ocrelizumab (any depleting monoclonal)	365 days ^b
Tocilizumab	60 days

Subjects required to take cholestyramine for 3 days and then subsequently at least 28 days of the washout period.

b All cytopenias must have recovered.

16.3 Lists of Prohibited Medications and Medications to be used with Caution

Table 16-1 Potential for Significant Drug Interactions: CYP3A and P-gp Inhibitors and Inducers Not to be administered from 14 days before first dose of study drug until 7 days after last dose of study drug*

Activity	Medication	VX-509 Dose Adjustment
Strong CYP3A Inhibitors	Antibiotic: clarithromycin, telithromycin HIV: indinavir, lopinavir/ ritonavir, nelfinavir, ritonavir, saquinavir HCV: boceprevir, telaprevir Anti-fungal: itraconazole, ketoconazole, voriconazole, posaconazole Calcium channel blocker: mibefradilb Phenylpiperazine anti-depressant: nefazodone Vasopressin receptor antagonist: conivaptan grapefruit, grapefruit juice	Prohibited
Moderate CYP3A Inhibitors	Antibiotic: ciprofloxacin, erythromycin HIV: Amprenavir, atazanavir, darunavir, fosamprenavir, ritonavir Anti-fungal: fluconazole Calcium channel blocker: diltiazem, verapamil Myeloproliferative: imatinib Substance P antagonist: aprepitant grapefruit, grapefruit juice ^a	Prohibited
Strong CYP3A Inducers	Cholesterol acyltransferase (ACAT) inhibitor: avasimibe ^b Anticonvulsant: carbamazepine, phenobarbital, phenytoin Anti-mycobacterial: rifabutin, rifampin St. John's wort ^c	VX-509 plasma concentrations will decrease more rapidly – not allowed in clinical trial
P-gp Inhibitors	Calcium channel blocker: verapamil Antibiotic: erythromycin Anti-fungal: itraconazole, ketaconazole Anti-arrhythmic: quinidine	Prohibited
P-gp Inducers	Anti-mycobacterial: rifampin St John's wort ^c	Prohibited

^{*} Please be advised that this list is not exhaustive. For an up to date list of CYP3A4 inhibitor medications, please refer to the following link: http://www.fda.gov/Drugs/DevelopmentApprovalProcess/ DevelopmentResources/DrugInteractionsLabeling/ucm093664.htm

a The effect of grapefruit juice varies widely among brands and is concentration-, dose-, and preparation-dependent. Studies have shown that it can be classified as a "strong CYP3A inhibitor" when a certain preparation was used (e.g., high strength) or as a "moderate CYP3A inhibitor" when another preparation was used (e.g., low strength).

b Withdrawn from the United States market for safety reasons.

c Herbal product.

Table 16-2 Potential for Significant Drug Interactions:

CYP3A Substrates

Not to be administered from 14 days before first dose of study drug until 7 days after last dose of study drug*

Alpha 1-adrenoreceptor antagonist

alfuzosin tamsulosin

Analgesics alternative: dextromorphan (with caution)

Alfentanil Buprenorphine Fentanyl

Lidocaine (systemic)

Methadone

Anti-arrhythmics (all Class I and Class III, including but not limited to the following examples):

Class I - quinidine, flecainide, propafenone

Other - bepridil

Antihistamines alternatives: loratadine, fexofenadine

astemizole terfenadine

Sedatives/anxiolytics alternatives (with caution): alprazolam, diazepam,

oral midazolam trazadone, midazolam IV

estazolam triazolam

Calcium channel blockers alternatives (with caution): amlodipine, diltiazem,

felodipine nicardipine, nifedipine, verapamil

nisoldipine

GI/GERD treatments alternative: metoclopramide

cisapride domperidone

Lipid lowering agents alternatives: pravastatin, rosuvastatin lovastatin alternative (with caution): atorvastatin

simvastatin

Phosphodiesterase type-5 inhibitors

sildenafil tadalafil vardenafil

Migraine alternatives: sumatriptan, zolmitriptan, frovatriptan

ergot derivatives (dihydroergotamine, ergotamine, ergonovine, methylergonovine)

eletriptan

Miscellaneous

colchicine cyclosporine

dronedarone alternative: cardioversion eplerenone alternative: spironolactone

pimozide alternatives: other antipsychotics (some with caution)

salmeterol

sirolimus/tacrolimus

Table 16-2 Potential for Significant Drug Interactions: CYP3A Substrates

Not to be administered from 14 days before first dose of study drug until 7 days after last dose of study drug*

telithromycin

alternative: azithromycin; other antibiotics approved for CAP

^{*} Please be advised that this list is not exhaustive. For any drug that is metabolized by CYP3A and not on this table, please check with Medical Monitor for guidance on coadministration. Note that this may also include certain dietary supplements including androgenic supplements.

Table 16-3 Medications To Be Used With Caution:

CYP3A Substrates

Dose reduction or limits to dosing frequency may be required in the presence of study drug*

Analgesics

dextromorphan

Calcium channel blockers

diltiazem

nicardipine

nifedipine

verapamil

Sedatives/anxiolytics

diazepam

trazadone

midazolam IV

Lipid lowering agents

atorvastatin

Miscellaneous

bosentan

budesonide

buspirone

dexamethasone

fluticasone

imatinib

saxagliptin

terbinafine

warfarin

voriconazole

zolpidem

^{*} Please be advised that this list is not exhaustive. For any drug that is metabolized by CYP3A but that is not on this table, please check with the Medical Monitor for guidance on coadministration. Note that this may also include certain dietary supplements including androgenic supplements.

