- 25. Subjects who require concomitant use of any moderate or strong inhibitors or inducers of CYP3A or P-gp or who require CYP3A substrates with serious associated side effects at high exposure (Section 10.3; partial lists in Section 16.3).
- 26. Have received a live or live attenuated vaccination in the 4 weeks before study Day 1.
- 27. Positive urine or serum pregnancy test.
- 28. Hemoglobin <11 g/dL for females or <12 g/dL for males at screening.
- 29. Absolute neutrophil count <1.5 K/μL at screening.
- 30. Platelet count <120 K/μL at screening.
- 31. ALT or AST \geq 1.5 × the ULN at screening.
- 32. Creatinine clearance <30 mL/min at screening
- 33. Positive hepatitis B surface antigen, hepatitis C virus antibody, or human immunodeficiency virus 1 and 2 antibodies at screening.
- 34. Other clinically significant out-of-range laboratory results in hematology, serum chemistry, coagulation studies, or urinalysis at the screening as judged by the investigator.

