10.3 Prior and Concomitant Medications and Other Study Restrictions

All medications (including herbal medicines and supplements) administered from 60 days before the Screening Visit through the Safety Follow-up Visit will be recorded in the source documents and on the electronic case report form (eCRF).

Subjects will be questioned at each study visit regarding use of medications during the period since the last visit. All medications used during the period will be recorded in the eCRF.

NSAIDs: Subjects may continue treatment with one NSAID (additional aspirin [second NSAID] ≤325 mg/day is allowed) at a dose that is stable for at least 28 days before Day 1, which must remain the same throughout the study. Any increase, decrease, or change in the dose of the one NSAID (not including aspirin) is prohibited during a subject's participation in the study, except for a dose reduction that is mandated for NSAID toxicity. NSAIDs are not stopped for the analgesic holiday before joint count assessments.

Systemic Corticosteroids: Subjects may continue treatment with prednisone ≤10 mg/day (or equivalent; Section 16.13), which must be a stable dose for at least 28 days before Day 1. Any increase, decrease, or change in the dose of systemic corticosteroid is prohibited during a subject's participation in the study, except for a dose reduction that is mandated for corticosteroid toxicity. Intraarticular corticosteroids are prohibited in any joint within 4 weeks before screening, and within 12 weeks before screening for the MRI-designated hand or joint planned for arthroscopy. Intraarticular corticosteroid injections are prohibited throughout the study (see Section 10.2), although this option may be discussed with the medical monitor if required to prevent early discontinuation (Section 9.1.4).

Live, Attenuated Vaccinations: Subjects who receive study drug should not receive any type of live or attenuated live vaccinations in the 4 weeks before study Day 1, during the study, or within 4 weeks after the final dose of study drug.

Drug-Drug Interactions: Any moderate or strong CYP3A or P-gp inhibitors or inducers as well as CYP3A sensitive substrates will be prohibited during the study; a partial list of prohibited medications is provided in Section 16.3.

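### Four drugs that Table 16-1 prohibits (diltiazem, verapamil, imatinib, voriconazole) appear in Table 16-3 as usable with caution, and Table 16-2 offers two of them as alternatives

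*Protocol*

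**What the plan says.** **The rule.** Exclusion 25 in Protocol Section 10.2 bars "Subjects who require concomitant use of any moderate or strong inhibitors or inducers of CYP3A or P-gp". Section 10.3 repeats this for the conduct of the trial: "Any moderate or strong CYP3A or P-gp inhibitors or inducers as well as CYP3A sensitive substrates will be prohibited during the study". Both sections refer to Section 16.3 for partial lists.

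**The prohibited list.** Table 16-1 covers CYP3A and P-gp inhibitors and inducers, which may not be given from 14 days before the first dose until 7 days after the last. Its moderate-inhibitor row includes "Calcium channel blocker: diltiazem, verapamil Myeloproliferative: imatinib". Its strong-inhibitor row includes "Anti-fungal: itraconazole, ketoconazole, voriconazole, posaconazole". Verapamil appears again as a P-gp inhibitor. All these rows are marked as prohibited.

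**The other two tables.** Table 16-2 lists CYP3A substrates that may not be given and, beside some of them, alternatives. For calcium channel blockers the text reads "Calcium channel blockers alternatives (with caution): amlodipine, diltiazem" and continues "felodipine nicardipine, nifedipine, verapamil". The second line runs two columns together: felodipine belongs to the barred column, and the other three names are alternatives. Table 16-3, headed "Table 16-3 Medications To Be Used With Caution", is a plain list that includes diltiazem, verapamil, imatinib and voriconazole.

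**The concern.** Section 16.3 is where a site looks to see whether a co-medication may be given. For these four drugs Table 16-1 says no and Table 16-3 says yes, with care. For diltiazem and verapamil, Table 16-2 goes further and suggests them.

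This matters because Section 9.2.6 says VX-509 is cleared mainly through CYP3A4. Table 16-3's only precaution is to lower the dose or frequency of the co-medication, which does nothing about reduced clearance of VX-509. Section 11.3 forbids study drug dose changes outside the biopsy subset, so most subjects could not have their VX-509 dose lowered to compensate. At stake are subject safety and adherence to Section 10.3. No sample size, power or error-rate figure is involved.

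**Working it through.** There is no statistical figure to reproduce. The check compares the three lists entry by entry and then tests them against the body text.

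**1. Status of each drug**

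| Drug | Table 16-1 | Table 16-2 | Table 16-3 |
|---|---|---|---|
| Diltiazem | Prohibited (moderate CYP3A inhibitor) | Alternative, with caution | Caution |
| Verapamil | Prohibited (moderate CYP3A inhibitor and P-gp inhibitor) | Alternative, with caution | Caution |
| Imatinib | Prohibited (moderate CYP3A inhibitor) | Not listed | Caution |
| Voriconazole | Prohibited (strong CYP3A inhibitor) | Not listed | Caution |

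**2. Share of Table 16-3.** The table has 1 analgesic + 4 calcium channel blockers + 3 sedatives or anxiolytics + 1 lipid-lowering agent + 11 miscellaneous drugs = 20. Four of them are prohibited in Table 16-1: 4/20 = 20%.

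**3. Share of the Table 16-2 calcium channel blocker alternatives.** These are amlodipine, diltiazem, nicardipine, nifedipine and verapamil, 5 in all. Two are prohibited in Table 16-1: 2/5 = 40%.

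**4. Overlaps that do not conflict.** Quinidine and telithromycin appear in both Tables 16-1 and 16-2, but each table bars them.

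**5. Is this an artefact of text extraction?** Table 16-2 is a two-column layout that has been run together. However, diltiazem stands on the line that introduces the alternatives, and Table 16-3, a single column, names both calcium channel blockers independently.

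**6. Does any text resolve the conflict?** Neither Section 10.3 nor Section 16.3 gives an order of precedence. Section 10.3 also advises caution, or a switch to another drug, for other CYP3A-metabolized medications, which leads a reader to Tables 16-2 and 16-3. The Table 16-3 footnote reads "For any drug that is metabolized by CYP3A but that is not on this table, please check with the Medical Monitor", so it does not reach drugs already on that table, which all four are. The Table 16-2 footnote likewise covers only drugs absent from its own table. Read literally it could reach imatinib and voriconazole, but Table 16-3 then supplies a permissive answer.

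**The case against.** The strongest reply is that the rule is not in doubt. Section 10.3 and exclusion 25 are categorical, Table 16-1 agrees with them, and both sections call the Section 16.3 lists partial. On that view the tables only illustrate a rule set elsewhere. This stands as to what was intended. It does not make the wrong entries right.

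A second reply is that the tables describe different directions of interaction. Table 16-1 is about other drugs acting on VX-509, while Tables 16-2 and 16-3 are about VX-509 acting on CYP3A substrates, and a drug can be both. This probably explains how the overlap arose. But a caution entry or a suggested alternative still reads as permission to give the drug.

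Third, Section 10.3 tells sites to take any question about concomitant medication to the medical monitor, and to contact the monitor when uncertain. Neither instruction is limited to unlisted drugs, and medications are reviewed at every visit. These are real safeguards, but the instructions to ask help only a site that sees there is a question. A site following a printed alternative may see none.

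Fourth, the practical reach is small. Exclusions 3, 4 and 6 make imatinib and voriconazole largely moot at entry, and exclusion 2 may, at the investigator's discretion, remove some users of calcium channel blockers. In a trial of about 40 subjects the live cases are chiefly diltiazem and verapamil, plus voriconazole for an infection that starts on study. This stands and limits the weight of the point.

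**Conclusion.** The concern holds. The protocol names four prohibited drugs as usable with caution and recommends two of them as substitutes, contrary to its own Table 16-1, Section 10.3 and exclusion 25. The percentages are shares of list entries, not of subjects or of drug exposure. The protocol gives no interaction size for any of the four, so nothing is claimed about VX-509 exposure, the safety margin or the dose comparison.

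The clearest route to harm is a subject on felodipine or nisoldipine, both barred by Table 16-2, who is switched to diltiazem or verapamil on the protocol's own suggestion. The conclusion rests on reading the caution and alternative entries as permission, which is how a site would ordinarily take them. It should be fixed: the error is in operative medication rules, concerns the main clearance pathway of the study drug, and costs little to correct.

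**What to change.** Keep the prohibition as it stands in Section 10.3, exclusion 25 and Table 16-1, and bring the other two tables into line:

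- Delete diltiazem, verapamil, imatinib and voriconazole from Table 16-3.
- Delete diltiazem and verapamil from the calcium channel blocker alternatives in Table 16-2. Amlodipine, nicardipine and nifedipine remain, with caution.
- While editing, add amlodipine to Table 16-3, since Table 16-2 offers it with caution but Table 16-3 omits it.
- Add one line to Section 16.3: Table 16-1 governs any drug that is both a CYP3A substrate and a listed CYP3A or P-gp inhibitor.
- Notify sites of the correction.

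The cost is an appendix correction and a site notification. Design, endpoints and analysis are untouched.

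### Tables 16-2 and 16-3 permit, with caution, drugs that Table 16-1, Section 10.3 and exclusion 25 prohibit: diltiazem, verapamil, imatinib and voriconazole

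*Protocol*

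**What the plan says.** Section 16.3 of the protocol holds three drug tables.

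- **Table 16-1** covers CYP3A and P-gp inhibitors and inducers, barred from 14 days before the first dose until 7 days after the last. The moderate CYP3A inhibitors include "Calcium channel blocker: diltiazem, verapamil Myeloproliferative: imatinib Substance P antagonist: aprepitant". The strong CYP3A inhibitors include "Anti-fungal: itraconazole, ketoconazole, voriconazole, posaconazole". The P-gp inhibitors include "Calcium channel blocker: verapamil Antibiotic: erythromycin". All three groups are marked as prohibited.
- **Table 16-2** covers CYP3A substrates barred over the same period and suggests substitutes. Its calcium channel blocker entry bars felodipine and nisoldipine. The substitutes run over two lines of the extracted text: "Calcium channel blockers alternatives (with caution): amlodipine, diltiazem", then "felodipine nicardipine, nifedipine, verapamil", where felodipine is the barred drug and the other three are substitutes.
- **Table 16-3** covers CYP3A substrates that may be used with caution, under the instruction "Dose reduction or limits to dosing frequency may be required in the presence of study drug". It names diltiazem, verapamil, imatinib and voriconazole. Its footnote reads "For any drug that is metabolized by CYP3A but that is not on this table, please check with the Medical Monitor".

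In the body text, exclusion 25 (Section 10.2) covers "Subjects who require concomitant use of any moderate or strong inhibitors or inducers of CYP3A or P-gp". Section 10.3 prohibits the same classes during the study, without exception, and refers to Section 16.3 for a partial list. Section 10.3 also sends questions and uncertainty about medication to the medical monitor.

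**The concern.** The same drug is forbidden in one table and allowed, or suggested as a substitute, in another. Site staff are likely to use these tables as look-up lists, and the answer depends on which one they open.

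The conflict concerns safety. Section 9.2.6 says that VX-509 is metabolised mainly through CYP3A4, so an inhibitor of that enzyme may raise VX-509 exposure. The advice in Table 16-3 does not address this. It treats the four drugs as substrates, whose own levels VX-509 may raise, and suggests adjusting their dose or frequency. The study drug dose cannot be lowered to compensate, because Section 11.3 prohibits dose modification outside the biopsy subset.

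There is also a conduct problem. A site that moves a subject from felodipine to diltiazem or verapamil, as Table 16-2 suggests, breaks Table 16-1 and Section 10.3.

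**Working it through.** There is no stated figure to reproduce. The check compares the lists drug by drug and then asks which text governs.

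**Step 1. Status of each drug in the three tables**

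| Drug | Table 16-1 | Table 16-2 | Table 16-3 |
|---|---|---|---|
| Diltiazem | Prohibited (moderate CYP3A inhibitor) | Offered as alternative, with caution | Caution |
| Verapamil | Prohibited (moderate CYP3A inhibitor; also P-gp inhibitor) | Offered as alternative, with caution | Caution |
| Imatinib | Prohibited (moderate CYP3A inhibitor) | Not named | Caution |
| Voriconazole | Prohibited (strong CYP3A inhibitor) | Not named | Caution |

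**Step 2. Extent of the overlap**

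- Table 16-3 names 20 drugs: 1 analgesic, 4 calcium channel blockers, 3 sedatives or anxiolytics, 1 lipid-lowering agent and 11 miscellaneous (1 + 4 + 3 + 1 + 11 = 20). Four are prohibited in Table 16-1: 4/20 = 20%.
- Of its 4 calcium channel blockers, 2 are prohibited: 2/4 = 50%.
- Table 16-2 offers 5 calcium channel blocker alternatives (amlodipine, diltiazem, nicardipine, nifedipine, verapamil). Two are prohibited: 2/5 = 40%.
- Table 16-2 names 21 drugs as alternatives in all. These two are the only ones in conflict (2 of 21).

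These are shares of list entries, not of subjects.

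**Step 3. Which text governs**

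No sentence ranks the tables, but the body text decides the matter. Table 16-1 classes all four drugs as moderate or strong CYP3A inhibitors. Exclusion 25 and Section 10.3 bar that class outright. Section 10.3 reserves caution for other CYP3A-metabolised drugs. Tables 16-2 and 16-3 are therefore the ones in error.

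**Step 4. Who could be affected**

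Exclusions 3 (cancer) and 4 (haematologic disorders) make imatinib unlikely at entry. Exclusion 6 (infection needing systemic antimicrobials) does the same for voriconazole. Either could still be started during the study. No comparable exclusion keeps out users of calcium channel blockers, apart from exclusion 25 itself and the general illness exclusion, so diltiazem and verapamil are the realistic cases.

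**Step 5. After correction**

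Table 16-3 keeps 20 − 4 = 16 drugs. The calcium channel blocker alternatives in Table 16-2 become 5 − 2 = 3. None of the remaining entries is named in Table 16-1.

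**The case against.** The strongest reply is that a drug can be both a substrate and an inhibitor. Tables 16-2 and 16-3 deal with what VX-509 does to other drugs, and Table 16-1 with what other drugs do to VX-509. On that view, a place on a substrate caution list does not lift a ban on inhibitors. This has some force for Table 16-3, although a list headed as usable with caution still reads as permission. It does not rescue Table 16-2, which puts forward two banned drugs as substitutes.

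Safeguards also exist: medication is asked about at every visit, and doubts go to the medical monitor. They help a site that notices the conflict. A site that finds diltiazem listed as an alternative has little reason to doubt it, and the Table 16-3 footnote sends only unlisted drugs to the monitor.

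A reader might infer two stronger claims. One is that the protocol leaves the rule open because no table is given precedence. That is not supported: exclusion 25 and Section 10.3 settle it. The other is that sites are directed to co-administer barred inhibitors. That too goes further than the text, which permits the drugs or offers them as alternatives, with caution, and instructs no one to give them.

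**Conclusion.** The contradiction is real: four drugs are prohibited by Table 16-1, Section 10.3 and exclusion 25, yet listed for cautious use in Table 16-3, and two of them are also offered as substitutes in Table 16-2. The clearest practical conflict is the calcium channel blocker entry in Table 16-2.

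The risk arises only if a site relies on Table 16-2 or 16-3 alone. It rests on the stated CYP3A4 metabolism of VX-509 and on Table 16-1's own classification of the four drugs. The protocol does not say how far an inhibitor would raise VX-509 exposure, or how many subjects take these drugs, so no size can be put on the harm. No endpoint, analysis or sample size is affected. The point is worth correcting because it is operative safety text and the correction costs almost nothing.

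**What to change.** Align the appendix with Table 16-1, Section 10.3 and exclusion 25:

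1. Delete diltiazem, verapamil, imatinib and voriconazole from Table 16-3.
2. Delete diltiazem and verapamil from the calcium channel blocker alternatives in Table 16-2, leaving amlodipine, nicardipine and nifedipine with caution.
3. Notify sites of the correction.

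The cost is six deletions in two appendix tables and one notice. Visits, sample size and analyses stay as they are. Checking the concomitant medication data already collected for the four drugs is optional.
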